5.0 Study Variables and Study Outcome Definitions

While clinical remission will be assessed in all patients irrespective of their status prebiologic initiation, response can only be assessed in patients impaired when initiating the treatment. Impairment will be defined for each domain independently as: 1) exacerbations: ≥2 exacerbations in the year preceding biologic initiation; 2) long-term OCS use: patients receiving long-term (daily) OCS at biologic initiation; 3) asthma symptoms control: partly or uncontrolled patients at biologic initiation, based on GINA 2020 asthma symptoms control categories (5); 4) lung function: patients <80% FEV1 predicted pre-biologic initiation.

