5.1 Individual response/remission domains

5.1.1 Exacerbation rates

Exacerbations during the follow-up will be counted from the day of the biologic initiation to the day closest to the 1-year mark post-initiation. A minimum of 48 weeks of follow-up will be required.

Response definition (in patients with ≥2 exacerbations in the year preceding biologic initiation)

Non-response: <50% reduction from pre- to post-biologic initiation
 Response: ≥50% reduction from pre- to post-biologic initiation

Post-biologic categories considered for remission definitions (in all patients, irrespective of pre-biologic status)

- ≥1 that required hospitalisation, or ≥3 of any severity
- 2 that did not require hospitalisation
- 1 that did not require hospitalisation
- None

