5.1.2 Long-term OCS use

Response definition (in patients receiving long-term OCS at biologic initiation)

Non-response: <50% reduction in daily dose from pre- to post-biologic initiation

• Response: ≥50% reduction in daily dose from pre- to post-biologic initiation

Post-biologic categories considered for remission definitions (in all patients, irrespective of pre-biologic status)

- >10mg/day
- >5 to 10mg/day
- >0 to 5mg/day
- No long-term OCS use

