5.2 Composite definitions of response/remission

5.2.1 Response

Eligibility criteria for impairment at biologic initiation and individual domain response definitions described in section 5.1 will be applied for the composite definitions of response. Levels of response will be defined for each composite definition by the number of single domain response criteria met as follows:

1) Exacerbation rates and long-term OCS use

Eligibility criteria: Patients with ≥2 exacerbations in the year preceding biologic initiation & receiving long-term OCS at biologic initiation

Response levels:

- Level 0: meeting none of the response criteria
- Level 1: meeting 1 of the response criteria
- Level 2: meeting both response criteria

2) Exacerbation rates, long-term OCS use, and asthma symptoms control

Eligibility criteria: Patients with ≥2 exacerbations in the year preceding biologic initiation

& receiving long-term OCS at biologic initiation

& being partly or uncontrolled at biologic initiation

Response levels:

Level 0: meeting none of the response criteria

Level 1: meeting 1 of the response criteria

· Level 2: meeting 2 response criteria

Level 3: meeting all 3 response criteria

3) Exacerbation rates, long-term OCS use, asthma symptoms control, and lung function*

Eligibility criteria: Patients with ≥2 exacerbations in the year preceding biologic initiation

& receiving long-term OCS at biologic initiation

& being partly or uncontrolled at biologic initiation

& having FEV1 <80% predicted at biologic initiation

Response levels:

• Level 0: meeting none of the response criteria

Level 1: meeting 1 of the response criteria

• Level 2: meeting 2 response criteria

• Level 3: meeting 3 response criteria

• Level 4: meeting all 4 response criteria

In order to explore composite definitions of response in non long-term OCS users, the variables defined above will be computed in this subgroup of patients after excluding the reduction in long-term OCS daily doses, ie 1) reduction in exacerbations and improvement in asthma symptoms control; and 2) reduction in exacerbations, improvement in asthma symptoms, and improvement in lung function. Other combinations of composite definitions of response (eg, improvement in asthma symptoms control and improvement in lung function alone) will also be explored.

^{*} The response criteria for improvement in lung function will primarily be an increase of at least 100mL in FEV1. Other criteria will be explored.

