5.3 Analytical variables

Table 4. List of variables that will be used for the analysis.

Label	Type	Value	Construct/comments
Meta data ¹			
Calendar year at biologic	Numerical	-	
initiation			
Follow-up duration	Numerical	-	At least 24 weeks and as close as
(weeks)			possible to 1 year
Biologic therapy variables ¹			
Type of biologics	Nominal	Anti-IgE, anti-IL5/5R, anti-IL4/13, anti-TSLP	
Biologic therapy	Binary	0=Switched/stopped	Data indicating a discontinuation of initial
maintenance	,	1=Continue	biologic in the first year of follow-up
Asthma-related outcome v	ariables ²		
Exacerbation rates			
Exacerbation rate at	Discrete	-	Number of exacerbations in the year
biologic initiation			preceding biologic initiation.
Rate of exacerbations	Discrete	-	Number of exacerbations requiring
requiring hospitalisation			hospitalisation in the year preceding
at biologic initiation			biologic initiation.
Exacerbation rate at	Discrete	-	Number of exacerbations during the year
follow-up			following biologic initiation.
Rate of exacerbations	Discrete	-	Number of exacerbations requiring
requiring hospitalisation			hospitalisation during the year following
at follow-up			biologic initiation.
Reduction of ≥50% in	Categorical	Yes	N/A for patients <2 exacerbations in the
exacerbation rate	3	No	year preceding biologic initiation.
between baseline and		N/A	, , , , , ,
follow-up			
Long-term OCS use ²	'		
Long-term OCS dose at	Numerical	-	Prednisone-equivalent dosages.
biologic initiation (mg/day)			
Long-term OCS dose at	Numerical	_	Prednisone-equivalent dosages.
follow-up (mg/day)	Numerical		Treumsone-equivalent dosages.
Reduction of ≥50% in	Categorical	Yes	N/A for patients not receiving long-term
long-term OCS dose	Categorical	No	OCS at biologic initiation
between baseline and		N/A	OGG at biologic illitiation
follow-up		19/7	
Asthma symptoms control ²	2		 
Asthma symptoms Asthma symptoms	Ordinal	Well controlled	GINA 2020 classification (used by most
control assessment at	Jidillal	Partly controlled	participating centres). For centres
biologic initiation		Uncontrolled	reporting asthma symptoms control
biologic iriliation		Oricontrolled	
			assessment based on ACT (52) and/or
			ACQ (53), algorithms will be used to fit
			available data to GINA 2020 categories: - ACQ:
			0.75< Mean ACQ <1.5: Partly controlled Mean ACQ ≥1.5: Uncontrolled
			- ACT: Total ACT >19: Well controlled
			15< Total ACT ≤19: Partly controlled
			Total ACT ≤15: Uncontrolled

		1	

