6.2 Sample size

As of 21 July 2022, a total of 5,961 patients who initiated biologics are recorded in ISAR.

All patients (objective 3)

Preliminary numbers of patients that will enter the remission analysis (objective 3) are presented in Figure 2. While pre-biologic status for the asthma-related outcomes is not a pre-requisite for the description of remission status, patients with no pre-biologic data overall will be excluded from the analysis as an important part of the project will be to characterize the patients at biologic initiation.

[figure not shown]

Figure 2. Preliminary flowchart of data availability for patients who initiated any type of biologics as of 21 July 2022. Exclusions are sequential from top to bottom.

In patients impaired at biologic initiation, by single domains and composite definitions of response (objective 2)

Table 5. Preliminary sample size of impaired patients at biologic initiation (numbers presented are patients who were impaired at biologic initiation and with available data at follow-up).

Domains	N
1. Exacerbations(≥2 exacerbation in the year preceding biologic initiation)	1,392
2. Long-term OCS dose (receiving long-term OCS at biologic initiation)	475
3. Asthma symptoms control (uncontrolled or partially controlled at biologic initiation)	1,360
4. Lung function (FEV ₁ <80% predicted at biologic initiation)	1,179
1+2	313
1+2+3	264
1+2+3+4	134

6.3 Analysis for objective 1

Objective 1 aims at describing the study population used in objectives 2 and 3. To this end, the pre-biologic asthma-related outcomes will first be described individually and in composite variables. For individual asthma-related outcomes, both continuous and categorical variables will be used. The categories will be based on the eligible criteria used for impairment:

- Exacerbations: ≥2 versus <2
- Long-term OCS use: yes/no
- Asthma symptoms control: partly or uncontrolled versus well controlled
- Lung function: ≥80% versus <80% FEV1 predicted

The distributions will be compared between initiated biologic class using t-tests, Kruskall Wallis tests, or Person's Chi-squared tests as appropriate. The distribution of pre-biologic asthma related outcomes will also be compared between countries (or geographic regions in case of small sample size).

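### The exploratory response composites for patients not on long-term OCS at initiation ignore follow-up OCS, so a patient newly on long-term OCS can be scored at the top response level

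*Protocol*

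**What the plan says.** Section 5.0 defines impairment in the OCS domain as "patients receiving long-term (daily) OCS at biologic initiation", so OCS status is fixed at initiation. Section 5.1.2 limits the OCS response to the same patients: "Response definition (in patients receiving long-term OCS at biologic initiation". Table 4 (section 5.3) sets the derived OCS response variable to "N/A for patients not receiving long-term" OCS at initiation, whatever the follow-up dose.

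The three numbered composites in section 5.2.1 Response all require long-term OCS at initiation. For non-users the section adds exploratory composites in which "the variables defined above will be computed in this subgroup of patients after excluding the reduction in long-term OCS daily doses". What remains is stated: "1) reduction in exacerbations and improvement in asthma symptoms control; and 2) reduction in exacerbations, improvement in asthma symptoms, and improvement in lung function". The scoring rule is a count: "Levels of response will be defined for each composite definition by the number of single domain response criteria met".

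Three other places bear on this:

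- Section 3.0 sets exacerbations and long-term OCS as the least that any composite must take into account.
- Section 5.1.2 lists follow-up OCS categories, including no use, for all patients regardless of baseline status. Section 5.2.1 Remission uses them in every definition.
- Table 4 lists the follow-up OCS dose in mg/day as a study variable.

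**The concern.** The remaining criteria are ones that new daily OCS could itself help a patient to meet. Section 1.0 describes OCS as giving rapid symptom relief and gives less OCS exposure as a reason for using biologics. If OCS is added after the biologic and the patient then improves, the improvement is credited in full and the added OCS does not enter the score. Compared with a rule that uses follow-up OCS, the omission can only raise a response level, never lower it.

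The aim in section 2.1 is to find the composites most useful for judging response, so the definitions are themselves a product of the study. Section 6.4 takes composite response levels as the outcome in regressions on patient characteristics and country or region, and does not set the exploratory composites apart. If new OCS use varies with those characteristics, the associations would absorb it.

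**Working it through.** **Step 1. Score one patient under the written rule, changing only the follow-up OCS dose.** The hypothetical patient has no long-term OCS and FEV1 below 80% predicted at initiation. The follow-up exacerbation did not need hospitalisation. Doses are illustrative.

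- Exacerbations fall from 4 to 1: (4 − 1)/4 = 75%. The criterion is "Response: ≥50% reduction from pre- to post-biologic initiation": met.
- Control moves from uncontrolled to well controlled, at least one category: met.
- FEV1 rises from 1,800 to 2,000 mL: +200 mL against the primary 100 mL threshold: met.

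| Follow-up long-term OCS (mg/day) | Exacerbations + symptoms | Exacerbations + symptoms + FEV1 | Relaxed remission, definition 1 |
|---|---|---|---|
| 0 | 2 of 2 | 3 of 3 | met |
| 5 | 2 of 2 | 3 of 3 | met |
| 10 | 2 of 2 | 3 of 3 | not met |
| 20 | 2 of 2 | 3 of 3 | not met |

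The response level does not depend on follow-up OCS at all; the remission result does. If exacerbations fell to 0 instead, strict remission definition 1 would be met at 0 mg/day and failed at 5, 10 and 20 mg/day, while response would stay at the top level throughout.

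**Step 2. Compare with a baseline OCS user.** A user going from 20 to 11 mg/day has a reduction of (20 − 11)/20 = 45%. That is below 50%, so this patient misses the top level of every numbered composite even with all other criteria met. A non-user going from 0 to 20 mg/day with the same other results reaches the top level of the non-user composites.

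**Step 3. Bound the pool.** Table 5 counts: "numbers presented are patients who were impaired at biologic initiation and with available data at follow-up".

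- Exacerbation-impaired: 1,392. Of these, in the composite with OCS: 313.
- Outside it: 1,392 − 313 = 1,079, or 1,079/1,392 = 78%.

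This is an upper bound on non-users, because it can also hold OCS users without follow-up OCS data and patients of unknown OCS status. The non-user composites also require symptom impairment, and the second requires FEV1 impairment. Table 5 gives these shares only among users: 264/313 for symptoms, and 134/313 for symptoms and FEV1. Assuming the same shares in the pool:

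- 1,079 × 264/313 ≈ 910 for the first composite.
- 1,079 × 134/313 ≈ 462 for the second.

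**Step 4. Apply assumed rates of new long-term OCS use.** The protocol gives none.

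| Assumed rate | of 1,079 | of 910 | of 462 |
|---|---|---|---|
| 1% | 10.8 | 9.1 | 4.6 |
| 3% | 32.4 | 27.3 | 13.9 |
| 5% | 54.0 | 45.5 | 23.1 |
| 10% | 107.9 | 91.0 | 46.2 |

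These are patients open to misclassification. Only those who meet every remaining criterion reach the top level. Assuming 50% to 70% do, the affected share of the pool runs from 0.01 × 0.50 = 0.5 to 0.10 × 0.70 = 7.0 percentage points. That is about 5 to 76 patients if the pool were the full 1,079.

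**The case against.** The strongest reply is that this is a deliberate design rule. Section 5.0 allows response to be assessed only in domains impaired at initiation, each domain taken separately. A patient well controlled at baseline is likewise not assessed for symptom response. A dose reduction cannot be computed from zero, so leaving the domain out is consistent. This explains why the reduction criterion is dropped. It does not explain why nothing takes its place when section 3.0 makes OCS part of the minimum and the follow-up dose is recorded.

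New OCS use is also visible elsewhere. The cross-tabulations in section 6.4 should show it, strict remission fails any new user, and relaxed remission fails those above 5 mg/day. That is correct, but none of these changes the response level.

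A reader might infer more than the protocol supports:

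- **That the main response results are inflated.** They are not: the numbered composites require OCS use at initiation and score the change in dose.
- **That treatment failures are generally turned into responders.** This is possible, not shown. Exacerbations are counted from the day of initiation, so those occurring before OCS was added count against the 50% reduction.
- **That about 1,079 patients are affected.** That is a ceiling on the pool, before further entry criteria and before any rate of new use.
- **That any new user should be a non-responder.** A baseline user whose dose rises loses one criterion and can still score on the others, and relaxed remission tolerates up to 5 mg/day. Level 0 or below would be harsher than both.

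The departure from section 3.0 could be read as a general sentence with an explicit exception. The protocol does not say so, and the two sections still need reconciling.

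**Conclusion.** The point holds for the exploratory non-user composites. As written, follow-up long-term OCS has no effect on their response levels, so new use is compatible with the top level, and the misclassification runs in one direction. The size is unknown. The pool is at most 1,079 patients; under the assumed ranges above, 0.5 to 7.0 percentage points of it would sit at the top level while on new long-term OCS.

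The conclusion rests on reading non-user status as status at initiation, as section 5.0 and Table 4 define it. If non-use at both time points were meant, the gap would close, but no text says this. It is worth correcting because the definition is fixed in the protocol, the data are already planned, and composite levels feed the regressions. It does not threaten the numbered composites.

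**What to change.** In section 5.2.1 Response, state how long-term OCS at follow-up enters the non-user composites. Either of two forms would do:

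- Make absence of long-term OCS at follow-up a requirement for the top level. A new user who meets all other criteria then falls below the top level but not to level 0. It should be a condition, not an extra point, because a point would give credit to every patient who simply stayed off OCS.
- Report patients newly on long-term OCS as a separate category, not counted among top-level responders.

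Also state that non-user status is taken at initiation, and reconcile this paragraph with section 3.0, either by bringing follow-up OCS in or by declaring the exception there.

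The cost is a sentence or two and one derivation condition on the follow-up dose in Table 4; no new data are needed. Patients without follow-up OCS data could not be classified at the top level under the first form, so their handling needs a line. Response proportions may become slightly less favourable. The change concerns how outcomes are classified, not how OCS is used.

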5.2.1 Remission

Composite definitions of remission will not impose pre-biologic impairments in any domains. The strict definitions will allow no exacerbation over the year following biologic initiation and no long-term OCS use at approximately 1 year after biologic initiation. The relaxed definitions will allow up to 1 exacerbation (not requiring hospitalisation) and up to 5mg/day of long-term OCS (a dose that can be used in patients who have adrenal insufficiency). Asthma symptoms control and lung function criteria will be progressively added as follows:

1) Exacerbation rates and long-term OCS use:

Strict definition:

no exacerbation in the year following biologic initiation

& no long-term OCS use at ~1 year following biologic initiation

Relaxed definition:

- ≤1 exacerbation (not requiring hospitalisation) in the year following biologic initiation
- & long-term OCS ≤5mg/day at ~1 year following biologic initiation

2) Exacerbation rates, long-term OCS use, and asthma symptoms control:

Strict definition:

- no exacerbation in the year following biologic initiation
- & no long-term OCS use at ~1 year following biologic initiation
- & partly/well controlled at ~1 year following biologic initiation

Relaxed definition:

- ≤1 exacerbation (not requiring hospitalisation) in the year following biologic initiation
- & long-term OCS ≤5mg/day at ~1 year following biologic initiation
- & partly/well controlled at ~1 year following biologic initiation

3) Exacerbation rates, long-term OCS use, asthma symptoms control, and lung function:

Strict definition:

no exacerbation in the year following biologic initiation

- & no long-term OCS use at ~1 year following biologic initiation
- & partly/well controlled at ~1 year following biologic initiation
- & FEV1 ≥80% predicted at ~1 year following biologic initiation

Relaxed definition:

- ≤1 exacerbation (not requiring hospitalisation) in the year following biologic initiation
- & long-term OCS ≤5mg/day at ~1 year following biologic initiation

& partly/well controlled at ~1 year following biologic initiation

& FEV1 ≥80% predicted at ~1 year following biologic initiation or stable lung function

5.3 Analytical variables

Table 4. List of variables that will be used for the analysis.

Label	Type	Value	Construct/comments
Meta data ¹			
Calendar year at biologic	Numerical	-	
initiation			
Follow-up duration	Numerical	-	At least 24 weeks and as close as
(weeks)			possible to 1 year
Biologic therapy variables ¹			
Type of biologics	Nominal	Anti-IgE, anti-IL5/5R, anti-IL4/13, anti-TSLP	
Biologic therapy	Binary	0=Switched/stopped	Data indicating a discontinuation of initial
maintenance	,	1=Continue	biologic in the first year of follow-up
Asthma-related outcome v	ariables ²		
Exacerbation rates			
Exacerbation rate at	Discrete	-	Number of exacerbations in the year
biologic initiation			preceding biologic initiation.
Rate of exacerbations	Discrete	-	Number of exacerbations requiring
requiring hospitalisation			hospitalisation in the year preceding
at biologic initiation			biologic initiation.
Exacerbation rate at	Discrete	-	Number of exacerbations during the year
follow-up			following biologic initiation.
Rate of exacerbations	Discrete	-	Number of exacerbations requiring
requiring hospitalisation			hospitalisation during the year following
at follow-up			biologic initiation.
Reduction of ≥50% in	Categorical	Yes	N/A for patients <2 exacerbations in the
exacerbation rate	3	No	year preceding biologic initiation.
between baseline and		N/A	, , , , , ,
follow-up			
Long-term OCS use ²	'		
Long-term OCS dose at	Numerical	-	Prednisone-equivalent dosages.
biologic initiation (mg/day)			
Long-term OCS dose at	Numerical	_	Prednisone-equivalent dosages.
follow-up (mg/day)	Numerical		Treumsone-equivalent dosages.
Reduction of ≥50% in	Categorical	Yes	N/A for patients not receiving long-term
long-term OCS dose	Categorical	No	OCS at biologic initiation
between baseline and		N/A	OGG at biologic illitiation
follow-up		19/7	
Asthma symptoms control ²	2		 
Asthma symptoms Asthma symptoms	Ordinal	Well controlled	GINA 2020 classification (used by most
control assessment at	Jidillal	Partly controlled	participating centres). For centres
biologic initiation		Uncontrolled	reporting asthma symptoms control
biologic iriliation		Oricontrolled	
			assessment based on ACT (52) and/or
			ACQ (53), algorithms will be used to fit
			available data to GINA 2020 categories: - ACQ:
			0.75< Mean ACQ <1.5: Partly controlled Mean ACQ ≥1.5: Uncontrolled
			- ACT: Total ACT >19: Well controlled
			15< Total ACT ≤19: Partly controlled
			Total ACT ≤15: Uncontrolled

		1	
Asthma symptoms	Ordinal	Well controlled	See above.
control assessment at		Partly controlled	
follow-up		Uncontrolled	
Improvement in asthma	Categorical	Yes	Yes:
symptoms control	22.29011001	No	Partially or uncontrolled → Well
between baseline and		N/A	controlled, or
follow-up		19/7	Uncontrolled → Partially controlled
ioliow-up			
			No: Remain uncontrolled or partially
			controlled
			N/A: Patients well controlled at baseline
Lung function ²			
Post-bronchodilator FEV ₁	Numerical	-	
at biologic initiation (mL)			
Post-bronchodilator FEV ₁	Numerical	_	
at follow-up (mL)	rtamonoai		
Post-bronchodilator FEV ₁	NI. una a mi a a l		
	Numerical	-	
percent predicted at			
biologic initiation			
Post-bronchodilator FEV ₁	Numerical	-	
percent predicted at			
follow-up			
Change in post-	Categorical	≥500mL increase	
bronchodilator FEV ₁	Janagariour	200 to 499mL increase	
between baseline and		100 to 199mL increase	
		Between 99mL	
follow-up			
		increase and 99mL	
		decrease	
		100 to 199mL decrease	
		≥200mL decrease	
Patient characteristics varia	ables		
Demographic characteristic			
Age at biologic initiation	Numerical	-	Attained age in complete years
(years)			/ mamou ago m complete yours
	Nominal	Female, male	
Sex			
Ethnicity	Nominal	Caucasian, South East	
		Caucasian, South East Asian, North East	
		Caucasian, South East Asian, North East Asian, African, Mixed,	
Ethnicity	Nominal	Caucasian, South East Asian, North East Asian, African, Mixed, Other, Unknown	
		Caucasian, South East Asian, North East Asian, African, Mixed, Other, Unknown Argentina, Australia,	
Ethnicity	Nominal	Caucasian, South East Asian, North East Asian, African, Mixed, Other, Unknown	
Ethnicity	Nominal	Caucasian, South East Asian, North East Asian, African, Mixed, Other, Unknown Argentina, Australia, Bulgaria, Canada,	
Ethnicity	Nominal	Caucasian, South East Asian, North East Asian, African, Mixed, Other, Unknown Argentina, Australia, Bulgaria, Canada, Colombia, Denmark,	
Ethnicity	Nominal	Caucasian, South East Asian, North East Asian, African, Mixed, Other, Unknown Argentina, Australia, Bulgaria, Canada, Colombia, Denmark, Greece, India, Ireland,	
Ethnicity	Nominal	Caucasian, South East Asian, North East Asian, African, Mixed, Other, Unknown Argentina, Australia, Bulgaria, Canada, Colombia, Denmark, Greece, India, Ireland, Italy, Japan, Kuwait,	
Ethnicity	Nominal	Caucasian, South East Asian, North East Asian, African, Mixed, Other, Unknown Argentina, Australia, Bulgaria, Canada, Colombia, Denmark, Greece, India, Ireland, Italy, Japan, Kuwait, Mexico, Poland,	
Ethnicity	Nominal	Caucasian, South East Asian, North East Asian, African, Mixed, Other, Unknown Argentina, Australia, Bulgaria, Canada, Colombia, Denmark, Greece, India, Ireland, Italy, Japan, Kuwait, Mexico, Poland, Portugal, Saudi Arabia,	
Ethnicity	Nominal	Caucasian, South East Asian, North East Asian, African, Mixed, Other, Unknown Argentina, Australia, Bulgaria, Canada, Colombia, Denmark, Greece, India, Ireland, Italy, Japan, Kuwait, Mexico, Poland, Portugal, Saudi Arabia, South Korea, Spain,	
Ethnicity	Nominal	Caucasian, South East Asian, North East Asian, African, Mixed, Other, Unknown Argentina, Australia, Bulgaria, Canada, Colombia, Denmark, Greece, India, Ireland, Italy, Japan, Kuwait, Mexico, Poland, Portugal, Saudi Arabia,	
Ethnicity	Nominal	Caucasian, South East Asian, North East Asian, African, Mixed, Other, Unknown Argentina, Australia, Bulgaria, Canada, Colombia, Denmark, Greece, India, Ireland, Italy, Japan, Kuwait, Mexico, Poland, Portugal, Saudi Arabia, South Korea, Spain,	
Ethnicity Country	Nominal	Caucasian, South East Asian, North East Asian, African, Mixed, Other, Unknown Argentina, Australia, Bulgaria, Canada, Colombia, Denmark, Greece, India, Ireland, Italy, Japan, Kuwait, Mexico, Poland, Portugal, Saudi Arabia, South Korea, Spain,	
Ethnicity	Nominal	Caucasian, South East Asian, North East Asian, African, Mixed, Other, Unknown Argentina, Australia, Bulgaria, Canada, Colombia, Denmark, Greece, India, Ireland, Italy, Japan, Kuwait, Mexico, Poland, Portugal, Saudi Arabia, South Korea, Spain,	Weight in kg/(height in m) ²
Ethnicity Country	Nominal	Caucasian, South East Asian, North East Asian, African, Mixed, Other, Unknown Argentina, Australia, Bulgaria, Canada, Colombia, Denmark, Greece, India, Ireland, Italy, Japan, Kuwait, Mexico, Poland, Portugal, Saudi Arabia, South Korea, Spain, Taiwan, UAE, UK, USA	Weight in kg/(height in m) ²
Ethnicity Country Body mass index (BMI) at biologic initiation	Nominal	Caucasian, South East Asian, North East Asian, African, Mixed, Other, Unknown Argentina, Australia, Bulgaria, Canada, Colombia, Denmark, Greece, India, Ireland, Italy, Japan, Kuwait, Mexico, Poland, Portugal, Saudi Arabia, South Korea, Spain, Taiwan, UAE, UK, USA	Weight in kg/(height in m) ²
Ethnicity Country Body mass index (BMI) at biologic initiation (kg/m²)	Nominal Nominal	Caucasian, South East Asian, North East Asian, African, Mixed, Other, Unknown Argentina, Australia, Bulgaria, Canada, Colombia, Denmark, Greece, India, Ireland, Italy, Japan, Kuwait, Mexico, Poland, Portugal, Saudi Arabia, South Korea, Spain, Taiwan, UAE, UK, USA	0 0 0 7
Ethnicity Country Body mass index (BMI) at biologic initiation (kg/m²) Body mass index at	Nominal	Caucasian, South East Asian, North East Asian, African, Mixed, Other, Unknown Argentina, Australia, Bulgaria, Canada, Colombia, Denmark, Greece, India, Ireland, Italy, Japan, Kuwait, Mexico, Poland, Portugal, Saudi Arabia, South Korea, Spain, Taiwan, UAE, UK, USA	Underweight: BMI<18.5
Ethnicity Country Body mass index (BMI) at biologic initiation (kg/m²) Body mass index at biologic initiation in	Nominal Nominal	Caucasian, South East Asian, North East Asian, African, Mixed, Other, Unknown Argentina, Australia, Bulgaria, Canada, Colombia, Denmark, Greece, India, Ireland, Italy, Japan, Kuwait, Mexico, Poland, Portugal, Saudi Arabia, South Korea, Spain, Taiwan, UAE, UK, USA - Underweight Normal weight	Underweight: BMI<18.5 Normal weight: 18.5≤BMI<25
Ethnicity Country Body mass index (BMI) at biologic initiation (kg/m²) Body mass index at	Nominal Nominal	Caucasian, South East Asian, North East Asian, African, Mixed, Other, Unknown Argentina, Australia, Bulgaria, Canada, Colombia, Denmark, Greece, India, Ireland, Italy, Japan, Kuwait, Mexico, Poland, Portugal, Saudi Arabia, South Korea, Spain, Taiwan, UAE, UK, USA - Underweight Normal weight Overweight	Underweight: BMI<18.5 Normal weight: 18.5≤BMI<25 Overweight: 25≤BMI<30
Ethnicity Country Body mass index (BMI) at biologic initiation (kg/m²) Body mass index at biologic initiation in	Nominal Nominal	Caucasian, South East Asian, North East Asian, African, Mixed, Other, Unknown Argentina, Australia, Bulgaria, Canada, Colombia, Denmark, Greece, India, Ireland, Italy, Japan, Kuwait, Mexico, Poland, Portugal, Saudi Arabia, South Korea, Spain, Taiwan, UAE, UK, USA - Underweight Normal weight Overweight Obesity class I	Underweight: BMI<18.5 Normal weight: 18.5≤BMI<25 Overweight: 25≤BMI<30 Obesity class I: 30≤BMI<35
Ethnicity Country Body mass index (BMI) at biologic initiation (kg/m²) Body mass index at biologic initiation in	Nominal Nominal	Caucasian, South East Asian, North East Asian, African, Mixed, Other, Unknown Argentina, Australia, Bulgaria, Canada, Colombia, Denmark, Greece, India, Ireland, Italy, Japan, Kuwait, Mexico, Poland, Portugal, Saudi Arabia, South Korea, Spain, Taiwan, UAE, UK, USA - Underweight Normal weight Overweight Obesity class I Obesity class II	Underweight: BMI<18.5 Normal weight: 18.5≤BMI<25 Overweight: 25≤BMI<30 Obesity class I: 30≤BMI<35 Obesity class II: 35≤BMI<40
Ethnicity Country Body mass index (BMI) at biologic initiation (kg/m²) Body mass index at biologic initiation in categories	Nominal Nominal Numerical Ordinal	Caucasian, South East Asian, North East Asian, African, Mixed, Other, Unknown Argentina, Australia, Bulgaria, Canada, Colombia, Denmark, Greece, India, Ireland, Italy, Japan, Kuwait, Mexico, Poland, Portugal, Saudi Arabia, South Korea, Spain, Taiwan, UAE, UK, USA - Underweight Normal weight Overweight Obesity class I Obesity class II Obesity class III	Underweight: BMI<18.5 Normal weight: 18.5≤BMI<25 Overweight: 25≤BMI<30 Obesity class I: 30≤BMI<35
Ethnicity Country Body mass index (BMI) at biologic initiation (kg/m²) Body mass index at biologic initiation in categories	Nominal Nominal	Caucasian, South East Asian, North East Asian, African, Mixed, Other, Unknown Argentina, Australia, Bulgaria, Canada, Colombia, Denmark, Greece, India, Ireland, Italy, Japan, Kuwait, Mexico, Poland, Portugal, Saudi Arabia, South Korea, Spain, Taiwan, UAE, UK, USA - Underweight Normal weight Overweight Obesity class I Obesity class II Obesity class III Current smoker, ex-	Underweight: BMI<18.5 Normal weight: 18.5≤BMI<25 Overweight: 25≤BMI<30 Obesity class I: 30≤BMI<35 Obesity class II: 35≤BMI<40
Ethnicity Country Body mass index (BMI) at biologic initiation (kg/m²) Body mass index at biologic initiation in categories Smoking status at biologic initiation	Nominal Nominal Numerical Ordinal	Caucasian, South East Asian, North East Asian, African, Mixed, Other, Unknown Argentina, Australia, Bulgaria, Canada, Colombia, Denmark, Greece, India, Ireland, Italy, Japan, Kuwait, Mexico, Poland, Portugal, Saudi Arabia, South Korea, Spain, Taiwan, UAE, UK, USA - Underweight Normal weight Overweight Obesity class I Obesity class II Obesity class III	Underweight: BMI<18.5 Normal weight: 18.5≤BMI<25 Overweight: 25≤BMI<30 Obesity class I: 30≤BMI<35 Obesity class II: 35≤BMI<40
Ethnicity Country Body mass index (BMI) at biologic initiation (kg/m²) Body mass index at biologic initiation in categories	Nominal Nominal Numerical Ordinal	Caucasian, South East Asian, North East Asian, African, Mixed, Other, Unknown Argentina, Australia, Bulgaria, Canada, Colombia, Denmark, Greece, India, Ireland, Italy, Japan, Kuwait, Mexico, Poland, Portugal, Saudi Arabia, South Korea, Spain, Taiwan, UAE, UK, USA - Underweight Normal weight Overweight Obesity class I Obesity class II Obesity class III Current smoker, ex-	Underweight: BMI<18.5 Normal weight: 18.5≤BMI<25 Overweight: 25≤BMI<30 Obesity class I: 30≤BMI<35 Obesity class II: 35≤BMI<40
Ethnicity Country Body mass index (BMI) at biologic initiation (kg/m²) Body mass index at biologic initiation in categories Smoking status at biologic initiation Asthma clinical features²	Nominal Nominal Numerical Ordinal	Caucasian, South East Asian, North East Asian, African, Mixed, Other, Unknown Argentina, Australia, Bulgaria, Canada, Colombia, Denmark, Greece, India, Ireland, Italy, Japan, Kuwait, Mexico, Poland, Portugal, Saudi Arabia, South Korea, Spain, Taiwan, UAE, UK, USA - Underweight Normal weight Overweight Obesity class I Obesity class II Obesity class III Current smoker, ex-	Underweight: BMI<18.5 Normal weight: 18.5≤BMI<25 Overweight: 25≤BMI<30 Obesity class I: 30≤BMI<35 Obesity class II: 35≤BMI<40 Obesity class III: BMI>40
Ethnicity Country Body mass index (BMI) at biologic initiation (kg/m²) Body mass index at biologic initiation in categories Smoking status at biologic initiation Asthma clinical features² Age of asthma onset	Nominal Nominal Numerical Ordinal	Caucasian, South East Asian, North East Asian, African, Mixed, Other, Unknown Argentina, Australia, Bulgaria, Canada, Colombia, Denmark, Greece, India, Ireland, Italy, Japan, Kuwait, Mexico, Poland, Portugal, Saudi Arabia, South Korea, Spain, Taiwan, UAE, UK, USA - Underweight Normal weight Overweight Obesity class II Obesity class III Current smoker, ex- smoker, never smoker	Underweight: BMI<18.5 Normal weight: 18.5≤BMI<25 Overweight: 25≤BMI<30 Obesity class I: 30≤BMI<35 Obesity class II: 35≤BMI<40 Obesity class III: BMI>40 Attained age in complete years at which
Ethnicity Country Body mass index (BMI) at biologic initiation (kg/m²) Body mass index at biologic initiation in categories Smoking status at biologic initiation Asthma clinical features²	Nominal Nominal Numerical Ordinal	Caucasian, South East Asian, North East Asian, African, Mixed, Other, Unknown Argentina, Australia, Bulgaria, Canada, Colombia, Denmark, Greece, India, Ireland, Italy, Japan, Kuwait, Mexico, Poland, Portugal, Saudi Arabia, South Korea, Spain, Taiwan, UAE, UK, USA - Underweight Normal weight Overweight Obesity class II Obesity class III Current smoker, ex- smoker, never smoker	Underweight: BMI<18.5 Normal weight: 18.5≤BMI<25 Overweight: 25≤BMI<30 Obesity class I: 30≤BMI<35 Obesity class II: 35≤BMI<40 Obesity class III: BMI>40 Attained age in complete years at which asthma was diagnosed or symptoms
Ethnicity Country Body mass index (BMI) at biologic initiation (kg/m²) Body mass index at biologic initiation in categories Smoking status at biologic initiation Asthma clinical features² Age of asthma onset (years)	Nominal Nominal Numerical Ordinal Numerical	Caucasian, South East Asian, North East Asian, African, Mixed, Other, Unknown Argentina, Australia, Bulgaria, Canada, Colombia, Denmark, Greece, India, Ireland, Italy, Japan, Kuwait, Mexico, Poland, Portugal, Saudi Arabia, South Korea, Spain, Taiwan, UAE, UK, USA - Underweight Normal weight Overweight Obesity class II Obesity class III Current smoker, ex- smoker, never smoker	Underweight: BMI<18.5 Normal weight: 18.5≤BMI<25 Overweight: 25≤BMI<30 Obesity class I: 30≤BMI<35 Obesity class II: 35≤BMI<40 Obesity class III: BMI>40 Attained age in complete years at which
Ethnicity Country Body mass index (BMI) at biologic initiation (kg/m²) Body mass index at biologic initiation in categories Smoking status at biologic initiation Asthma clinical features² Age of asthma onset	Nominal Nominal Numerical Ordinal	Caucasian, South East Asian, North East Asian, African, Mixed, Other, Unknown Argentina, Australia, Bulgaria, Canada, Colombia, Denmark, Greece, India, Ireland, Italy, Japan, Kuwait, Mexico, Poland, Portugal, Saudi Arabia, South Korea, Spain, Taiwan, UAE, UK, USA - Underweight Normal weight Overweight Obesity class II Obesity class III Current smoker, ex- smoker, never smoker	Underweight: BMI<18.5 Normal weight: 18.5≤BMI<25 Overweight: 25≤BMI<30 Obesity class I: 30≤BMI<35 Obesity class II: 35≤BMI<40 Obesity class III: BMI>40 Attained age in complete years at which asthma was diagnosed or symptoms

Asthma duration	Numerical	-	Whole years between age of asthma onset and biologic initiation
Highest blood eosinophil count before biologic initiation (10 ⁹ cells/L)	Numerical	-	
Highest blood IgE count before biologic initiation (IU/mL)	Numerical	-	
Highest FeNO test before biologic initiation (ppb)	Numerical	-	
Allergy test results before biologic initiation	Binary	Positive, negative	From skin prick test or serum test for dust mite, grass mix, cat hair, mould mix, dog hair, aspergillus, weed mix, trees, food mix, animal mix, or other environmental allergens
Asthma-related medication	at biologic init	iation ²	1
Long-acting muscarinic antagonist (LAMA) in the year preceding biologic initiation	Binary	Yes, no	
Theophylline in the year preceding biologic initiation	Binary	Yes, no	
Leukotriene receptor antagonist (LTRA) in the year preceding biologic initiation	Binary	Yes, no	
Macrolide antibiotic in the year preceding biologic initiation	Binary	Yes, no	
Other steroid sparing agents in the year preceding biologic initiation	Binary	Yes, no	
Other treatment in the year preceding biologic initiation	Binary	Yes, no	
History of comorbidities at			
Allergic rhinitis ²	Binary	Yes, no	
Chronic rhinosinusitis ²	Binary	Yes, no	
Nasal polyps ² Eczema/atopic dermatitis ²	Binary Binary	Yes, no Yes, no	
Sleep apnea ³	Binary	Yes, no	
Anxiety/depression ³	Binary	Yes, no	
Osteoporosis ³	Binary	Yes, no	
Diabetes ³	Binary	Yes, no	
Chronic heart disease ³	Binary	Yes, no	
Pneumonia ³	Binary	Yes, no	
Peptic ulcer ³ Pulmonary embolism/ venous	Binary Binary	Yes, no Yes, no	
thromboembolism ³			
Cataract ³	Binary	Yes, no	
Chronic kidney disease ³	Binary	Yes, no	
Glaucoma ³	Binary	Yes, no	
Cerebrovascular accident ³	Binary	Yes, no	

- 1. Core ISAR variables.
- 2. Core ISAR variables, although not necessarily available pre-biologic initiation if biologic initiation occurred before enrolment visit.
- 3. Effectiveness bolt-on variables, collected by a selection of participating countries.

